6. STATISTICAL ANALYSES

Note that standard data derivation rule and stat methods are described in Section 11 and will not be repeated below.

6.1. Demography

6.1.1. Analysis of demographics/baseline characteristics planned in the protocol

Demographic and baseline characteristics: age (in years), gender, ethnicity, smoking status at enrolment (i.e., screening visit) will be summarised by group using descriptive statistics.

Other variables GOLD grade at baseline, history of moderate and severe exacerbation in the last 12 months (<2 or ≥ 2 , and total number), HRQOL baseline scores from CAT, SGRQ-C at enrolment visit (i.e., screening visit) will also be summarized as baseline characteristics.

- Frequency tables will be generated for categorical variable such as gender; geographical ancestry, age category, GOLD, smoking status and history of moderate and severe exacerbation;
- N, mean, median, standard deviation (SD) and min and max values will be provided for continuous data such as age, height, weight, body mass index (BMI), total number of exacerbation in previous 12 months and HRQOL baseline scores.

The following variables will be included in demography summary and listings:

- Age in year (as continuous variable),
- Age category: 40-59 y, 60-80y
- Gender: Male, Female
- Race: (all reported in e-CRF)
- Ethnicity: Hispanic or Latino, Not Hispanic nor Latino
- Exacerbations in previous 12 months:
 - Total number
 - Mild
 - Moderate
 - Severe
- Exacerbations in previous 12 months category: <2, ≥ 2
- Smoking status: yes, no
- Pack year (as continuous variable)

CONFIDENTIAL

207489 (NTHI MCAT-002)

Statistical Analysis Plan Amendment 2 FDA Final Draft

- GOLD grade category: 1 mild, 2 moderate, 3 severe, 4 very severe
- FE1/FVC category: ≥ 70 , < 70
- CMI sub-cohort: yes, no
- Culture cohort: yes, no

The following variables will be included in vital sign summary and listing:

- Height (cm)
- Weight (kg)
- Body temperature (continuous variable)
- Body temperature category $< 37.5^{\circ}\text{C}$, $\geq 37.5^{\circ}\text{C}$
- Heart rate
- Respiratory rate
- Systolic Blood Pressure,
- Diastolic Blood Pressure,
- Chest x-ray result: yes, no
 - Infiltrate presence (%): unilateral, bilateral
 - Pleural effusion (%): right chest, left chest, bilateral

Demographic and baseline characteristics will be tabulated for the Exposed Set (TVC) and mTVC, and no inferential analyses are planned.

The distribution of subjects enrolled among the study sites and country will be tabulated as a whole and per group.

Number and percentages of subjects in each study cohorts (All enrolled, TVC, mTVC, FAS and PPS) will be summarized by group.

Withdrawal status will be summarised by group using descriptive statistics:

- The numbers of withdrawn subjects will be tabulated according to the reason for withdrawal;
- The number of subjects enrolled into the study as well as the number of subjects excluded from any cohort of analyses will be tabulated.

CONFIDENTIAL

207489 (NTHI MCAT-002)

Statistical Analysis Plan Amendment 2 FDA Final Draft

6.1.2. Additional considerations

Physical examination:

- As part of the baseline characteristics, variables collected during the physical examination such as height, weight, BMI, pulmonary function test baseline values (such as FEV₁/FVC, FEV₁ and FEV₁ % of predicted), body temperature, heart rate, respiratory rate, Systolic blood pressure (SBP) and diastolic blood pressure (DBP) values will be summarized by the mean of descriptive statistics.

Body temperature will be also categorized as Fever YES ($\geq 37.5^{\circ}\text{C}$ (99.5°F)) or NO ($< 37.5^{\circ}\text{C}$ (99.5°F))

Haematology profile:

Haematology profile is defined at visit 1 only and the following parameters will be analysed from whole blood:

Whole blood	Leukocytes (White Blood Cells) Neutrophils Lymphocytes Eosinophils Basophils Monocytes Erythrocytes (Red Blood Cells) Hemoglobin Platelets
-------------	--

For each group and for each **haematology parameter** descriptive statistics such as: mean, median, standard deviation, minimum and maximum will be tabulated, together with the percentage of subjects having results below or above laboratory normal ranges.

Vaccination and Medical History

- The frequencies and percentages of subjects with medical history and by MedDRA body system and preferred term will be presented overall and by vaccine group.
- Similarly, the frequencies and percentage of subject who received influenza or pneumococcal vaccination in the previous 12 months before enrollment will be reported overall and by vaccine group

6.2. Exposure**6.2.1. Analysis of exposure planned in the protocol**

The frequencies and percentages of subjects with vaccinations will be summarized overall and by vaccine group. Data will be tabulated for the Exposed Set.

6.2.2. Additional considerations

None.

CONFIDENTIAL

207489 (NTHI MCAT-002)

Statistical Analysis Plan Amendment 2 FDA Final Draft

6.3. Efficacy/Effectiveness

Efficacy of the vaccine will be evaluated as both primary and secondary endpoints.

In the primary endpoint analysis, the ‘clinical’ vaccine efficacy is defined as reduction in 12 months rate of moderate and severe AECOPD (any cause) from one month after complete vaccine exposure.

In secondary endpoints a broader definition for efficacy is being investigated and the following rates are considered:

- Reduction in 3, 6, and 9 months rate of moderate and severe of AECOPD (any cause) starting from one month after complete vaccine exposure.
- Reduction in yearly rate of any grading of AECOPD (any cause) starting from one month after complete vaccine.
- Reduction in severity of AECOPD (any cause) starting from one month after complete vaccine.
- Reduction in yearly rate of moderate and severe of AECOPD associated with NTHi or Mcat, starting from one month after complete vaccine.
- Reduction in yearly rate of any grading of AECOPD associated with NTHi or Mcat, starting from one month after complete vaccine.
- Reduction in 3, 6, and 9 months rate of moderate and severe AECOPD associated with NTHi or Mcat starting from one month after complete vaccine exposure.
- Reduction in severity of AECOPD associated with NTHi or Mcat starting from one month after complete vaccine.

6.3.1. Analysis of efficacy planned in the protocol

The efficacy analysis will be performed on the mTVC and repeated on the TVC and on the FAS. The primary efficacy analysis will also be repeated on the PPS if the percentage of vaccinated subjects excluded from the PPS for efficacy is more than 5%.

In the TVC cohort, if a subject receives only one dose the efficacy endpoint is defined as the number of (moderate or severe) AECOPD (any cause), occurring within a period starting from Day 90 and lasting for 1 year (i.e., until study conclusion).

Vaccine efficacy (VE) is expected to start at 1 month post-Dose 2 (Day 90), so the study period is divided in to two: from enrolment (Day 1 - day of first injection) up to one month post Dose 2 (Day 90) and from one month post Dose 2 (Day 90) until study end (Day 451).

Evaluation of VE and incidence rate of AECOPD in both study groups, together with CIs will be computed for each study periods.

CONFIDENTIAL

207489 (NTHI MCAT-002)

Statistical Analysis Plan Amendment 2 FDA Final Draft

6.3.1.1. Efficacy – Clinical Endpoints**6.3.1.1.1. Primary Analyses**

The primary analysis method of the vaccine VE will consider the exact inference on the risk ratio (R_{vacc} / R_{con}) based the total number of moderate and severe AECOPD observed in 1 year time of follow up.

VE is defined as: $VE = 1 - R_{vacc} / R_{con}$

being

- R_{vacc} = average yearly incidence rate of AECOPD events per subject in the group 10-10-3-AS.
- R_{con} = average yearly incidence rate of AECOPD events per subject in the placebo group.

Inferential statistic

Incidence rates and VE with 87% and 95% CIs will be tabulated for primary efficacy endpoint. P-value (to test $H_0 = [VE=0]$) will be tabulated for the primary endpoint.

The efficacy of vaccine in preventing moderate and severe AECOPD will be demonstrated if the lower limit of the two-sided 87% CI of VE is above 0.

The primary outcome will be analysed using the Negative Binomial regression model with number of AECOPD as dependent variable; treatment (vaccine or placebo), age group (40 - 59 yrs or 60 - 80 yrs), GOLD grade (2, 3 or 4) and history of moderate and severe exacerbations (<2 or ≥ 2) and country as independent variables, with logarithm as link function, and the logarithm of time for follow-up (in days) as an offset variable.

The following SAS code will be applied for primary analysis:

```
PROC GENMOD data=<dataset>;
  CLASS trt age gold hexac country;
  MODEL nb_exac = trt age gold hexac country
    / dist=NegBin LINK=log OFFSET=logfu alpha=0.13;
RUN;
```

Where

trt= treatment arm;
 age= Age Group;
 nb_exac=number of exacerbations;
 gold= GOLD grade at enrolment;
 hexac= History of moderate/severe exacerbation;
 country=Subject Country;
 fu= follow up time in days;
 logfu= log(fu);

CONFIDENTIAL

207489 (NTHI MCAT-002)

Statistical Analysis Plan Amendment 2 FDA Final Draft

Point estimate and CIs of the incidence rate for each arm, will be computed using a simple Negative Binomial model, without covariates and thus the following SAS code will be applied:

```

PROC GENMOD data=<dataset>;
BY trt;
MODEL nb_exac =           / dist =NegBin LINK=LOG OFFSET=LOGFU alpha=0.05;
ODS OUTPUT ParameterEstimates=out_parm NObs=Nobs;
RUN;

DATA parm_est(keep= val rate rate_LL rate_UL);
SET out_parm(WHERE=(Parameter='Intercept'));
format rate rate_LL rate_UL 8.2;
val= "Yearly Rate from Negative Binomial";
rate=EXP(Estimate)*365;
rate_LL=EXP(LowerWaldCL)*365;
rate_UL=EXP(UpperWaldCL)*365;
RUN;

```

Note: If the model does not converge, the Poisson distribution will be used instead of the Negative Binomial.

The number of AECOPD occurring from enrolment up to 1 month post-Dose 2 will be used as ‘baseline’ value. No difference between vaccine and placebo is expected in this period.

Descriptive statistics

For each treatment group, the total number of subjects, total number of AECOPD, total exposure time (in days), and incidence exacerbation rate (per year and per each sub period considered) together with the frequency of number of AECOPD will be tabulated.

The following statistics will be reported for exacerbation rate in the two treatment groups: N, mean, SD, median, Q1, Q3, min and max.

Sensitivity analysis

Primary analysis will be presented in three study populations: mTVC, TVC, FAS and PPS. In addition, a sensitivity analysis will be carried out using permutation test.

Permutation test procedure

The null distribution of Z to test H_0 (i.e., $\beta=0$ or $VE=0$) will be obtained by re-randomizing treatment assignment according to the original minimization algorithm (Section 11.3) while keeping outcomes and covariates as observed. The procedure to follow is described below:

1. Fit the regression model to obtain the test statistic Z to test H_0 (i.e., $\beta=0$ or $VE=0$)
2. Estimate the null distribution for the test statistic Z with N (=10000) replicates of the two following steps:

CONFIDENTIAL

207489 (NTHI MCAT-002)

Statistical Analysis Plan Amendment 2 FDA Final Draft

- a. Re-randomize treatment assignment using minimization.
- b. Re-fit the regression model to re-derive the test Z
- 3. Derive the empirical p-value for the test statistic Z from the null distribution based on the permutation distribution

$$p(\text{permutation test}) = (M)/(N)$$

Where M denotes the number of replicates for which the test statistic Z obtained in the permutation procedure is equal to or greater than (in absolute value) the observed value of Z obtained in 1, and N denotes the number of replicates (i.e., 10000).

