2. STUDY DESIGN

Figure 1 Study design overview

S = Screening Visit; V = Visit; PC = Phone contact; D = Day; FU = Follow-up; BS (1) = blood sample for humoral immunogenicity; BS (2) = blood sample for cell-mediated immunogenicity (CMI), this blood sample will only be collected from a sub-cohort of subjects; BS (3) blood sample for biomarkers; SP = sputum sample

The allowed maximum interval between Screening Visit and Visit 1 is 29 days. If a delay occurs for an eligible subject so that the interval exceeds 29 days, some study procedures performed during the Screening Visit needs to be repeated within 7 days (see Table 6 of the protocol for more details).

* An AECOPD visit should be scheduled as soon as possible after the onset of AECOPD symptoms (max 96 hours after and, if applicable, preferably before starting treatment with antibiotics) During this visit blood and sputum samples will be collected. In addition, follow-up phone call(s) and/or visit(s) will take place to determine the end of the AECOPD. These contacts will take place at least every 2 weeks until the AECOPD is resolved.

Investigational vaccine and placebo will be administered in addition to standard of care.

- **Experimental design:** Phase IIB, randomised, observer-blind, placebo-controlled, multi-centric study with two parallel groups.
- **Duration of the study:** for each subject enrolled, the study will last approximately 15 months from Visit 1 up to study completion (Visit 8).
 - Epoch 001: Screening Visit (Day -28 to Day -1).
 - Epoch 002 : Primary starting at Visit 1 (Day 1) and ending at Visit 8 (Day 451).
- **Primary completion Date (PCD):** Last Subject Last Visit (LSLV) from Visit 8 (Day 451) or last visit/contact of Epoch 002.
- **Study groups:**
 - **10-10-3-AS:** Approximately 300 subjects receiving two doses of the AS01_E-adjuvanted GSK Biologicals' NTHi-Mcat investigational vaccine containing 10 µg of PD, 10 µg of PE-PilA, and 3.3 µg of UspA2.
 - **CONTROL:** Approximately 300 subjects receiving two doses of placebo (PBS).

CONFIDENTIAL

207489 (NTHI MCAT-002)

Statistical Analysis Plan Amendment 2 FDA Final Draft

The following group names will be used for the statistical analysis

Table 1 Study groups and epochs foreseen in the study

Group order in tables	Number of subjects	Group label in tables	Group definition for footnote
1	~300	10-10-3-AS	2 doses of AS01E-adjuvanted NTHI/Mcat vaccine containing 10 mcg of PD, PE-PiA and 3 mcg of UspA2

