6.3.2. Additional considerations

6.3.2.1. Clinical endpoint

Number of AECOPD

The number of AECOPD occurring during the 1 year follow-up period starting 1 month post-Dose 2 will be used to describe vaccine efficacy (VE). Exacerbation rate reported during this period will be calculated for each subject.

Only for the purpose of reporting summary statistics, the number of exacerbations during the 1-year follow-up will be imputed for subjects withdrawing from the study to provide an estimate of the number of exacerbations over the follow-up period. This calculation will only be performed for the descriptive statistics for the rate of exacerbations during 1 year follow up period since the modelling of exacerbations takes into account the number of exacerbations and the time of follow-up for each subject [see Section 11].

Control of type I error

Inferential analyses for efficacy are planned to be performed at alpha level of 0.13 (two sided). No alpha adjustment for multiple testing in the secondary endpoints will be performed, nevertheless efficacy analysis, both primary and secondary endpoints will be also complemented with the 95% CI.

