11.3. Randomization method and minimization algorithm

Subjects are randomised using a centralised randomisation system on internet (SBIR) at first dose. The system incorporates a minimization algorithm based on White SJ and Freedam LS method [[White SJ](#), Freedman LS, 1978] and it is described below:

Notation:

- k input values to be used for minimization, each with a weight w_k ($k=1, \dots, K$) and l_k variants.
- i treatment groups applicable to stratum the subject has been identified with randomization ratio a_1, \dots, a_i
- D: percentage of determinism
- W: weight assigned to each minimization factor

In this study k=4: Country, GOLD grade, History of exacerbation and Age group defined as :

COUNTRY [8 variants]: BE CA FR DE IT ES UK US

GOLD [3 variants]: 2 3 4

AGECAT [2 variants]: 40-60 61-80

HIST_ES [2 variants]: < 2 >=2

i=2: VACCINE and PLACEBO with randomization ratio 1:1 ($a_i=1$)

D=90%

W=1 for each variable

CONFIDENTIAL207489 (NTHI MCAT-002)
Statistical Analysis Plan Amendment 2 FDA Final Draft

Algorithm:

For a new subject in criteria levels $s_1 \dots s_k$ **Step 1: Minimization computation**

Step 1.1: Initialize Problem flag to 0

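### Section 6.3.1.1.1 names two primary methods and does not say which supplies the 87% interval; the exact method, on its usual reading, and the uncorrected Poisson fallback both ignore overdispersion

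*SAP*

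**What the plan says.** All references are to the current SAP (Amendment 2).

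Section 6.3.1.1.1 makes two statements about the primary method. The first is "The primary analysis method of the vaccine VE will consider the exact inference on the risk ratio", with the ratio formed from the total number of moderate and severe AECOPD over one year. The second, a few lines later, is "The primary outcome will be analysed using the Negative Binomial regression model with number of AECOPD as dependent variable", adjusted for age group, GOLD grade, exacerbation history and country, with log follow-up time as offset. The GENMOD code given for the primary analysis carries the options "dist=NegBin LINK=log OFFSET=logfu alpha=0.13".

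Between the two stands the success rule: efficacy is "demonstrated if the lower limit of the two-sided 87% CI of VE is above 0". No sentence says which method produces that interval, and no exact procedure is named or coded anywhere.

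A note after the code adds: "If the model does not converge, the Poisson distribution will be used instead of the Negative Binomial". It gives no scale parameter or robust variance. The sensitivity part of the section plans a re-randomisation test with 10,000 replicates. Section 6.3.1.2 applies the same model to the bacteriological endpoint. The sentence on exact inference stands in all three SAP versions in the file, so amendment has not removed it.

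**The concern.** A primary decision rule should point to one interval. Here two incompatible methods each carry the label primary, and they can disagree.

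The usual exact inference on two event totals conditions on their sum and treats the split as binomial, which is valid only if counts have variance equal to the mean. Plain Poisson regression makes the same assumption. By choosing a negative binomial model, the SAP allows for subjects who differ in their underlying exacerbation rate, and in that case both alternatives give limits that are too narrow. At stake is whether the 87% limit that decides success has its stated error rate, and whether the choice of interval is closed before unblinding.

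**Working it through.** **Inputs from the SAP.** Two-sided alpha 0.13 (Sections 6.3.2.1 and 7); 87% interval (6.3.1.1.1); about 300 per arm (Section 2); 1:1 allocation (11.3); one year of follow-up from one month after Dose 2 (4.1).

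**Assumed, because the SAP does not state them.** Mean 0.5, 1.0 or 1.5 events per subject-year; negative binomial dispersion k from 0 to 1.0, with variance = mean × (1 + k × mean); complete follow-up; true VE = 0.

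**Stated level.** 1 − 0.87 = 0.13, and the two-sided critical value is z = 1.514. The interval and alpha agree. Success is defined in one direction, so the nominal risk of a false efficacy claim is 0.13 / 2 = 6.5%.

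**Closed form.** With n per arm and common mean μ, the Poisson standard error of the log rate ratio is √(2/(nμ)). The negative binomial one is √(2(1 + kμ)/(nμ)). Their ratio is √(1 + kμ), so n cancels and a larger trial would not cure the problem. The actual two-sided error of a nominal 13% Poisson Wald test is

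2 × [1 − Φ(1.514 / √(1 + kμ))].

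- kμ = 0.3: 1.514 / 1.140 = 1.328, giving 18%.
- kμ = 1.5: 1.514 / 1.581 = 0.958, giving 34%.

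**Simulation under VE = 0, 300 per arm.** 20,000 trials per row for the exact conditional test and both Poisson versions; 1,500 for the negative binomial model (Monte Carlo standard error about 0.9 points). Entries are two-sided rejection rates in %, nominal 13.

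| Mean | k | Exact on totals | Plain Poisson | Closed form | Pearson-scaled Poisson | Negative binomial |
|---|---|---|---|---|---|---|
| 0.5 | 0 | 12.0 | 13.3 | 13.0 | 13.3 | 13.3 |
| 0.5 | 0.25 | 13.9 | 15.5 | 15.3 | 13.0 | 13.3 |
| 0.5 | 0.5 | 15.8 | 17.3 | 17.6 | 12.9 | 13.4 |
| 0.5 | 1.0 | 20.4 | 22.0 | 21.6 | 13.4 | 14.1 |
| 1.0 | 0 | 12.0 | 13.1 | 13.0 | 13.1 | 13.3 |
| 1.0 | 0.25 | 16.8 | 17.8 | 17.6 | 13.4 | 13.1 |
| 1.0 | 0.5 | 20.6 | 21.8 | 21.6 | 12.8 | 12.8 |
| 1.0 | 1.0 | 26.9 | 28.1 | 28.4 | 13.0 | 12.7 |
| 1.5 | 0 | 12.5 | 13.2 | 13.0 | 13.4 | 13.5 |
| 1.5 | 0.25 | 18.6 | 19.6 | 19.7 | 12.9 | 11.9 |
| 1.5 | 0.5 | 24.3 | 25.3 | 25.2 | 13.1 | 11.6 |
| 1.5 | 1.0 | 33.1 | 34.1 | 33.8 | 13.2 | 12.8 |

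For means of 1.0 to 1.5 and k of 0.3 to 1.0, the exact test runs at about 17% to 33% and plain Poisson at about 18% to 34%. With equal arms and VE = 0 the two directions are equally likely, so the false-efficacy risk is half of this: 17 / 2 = 8.5 and 34 / 2 = 17, or roughly 8% to 17%.

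**Effect of covariates.** The fallback would keep the covariates. With one covariate explaining 25% to 50% of the heterogeneity, Poisson still rejected in 15.5% to 26.0% of trials (1,200 per scenario).

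**How often the fallback would be reached.** A dispersion estimate at zero served as proxy for non-convergence. It occurred in 0% to 3.7% of overdispersed trials, and in 0% at means of 1.0 and 1.5. It was common (52% to 54%) only at k = 0, where Poisson is valid.

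**The case against.** The strongest reply is that the operative analysis can be identified. The negative binomial paragraph is followed by code expressly for the primary analysis, at alpha 0.13. That code is the only place where an 87% interval is computed. The re-randomisation procedure starts from the test statistic of the regression model, and Section 6.3.2.1 says that the modelling accounts for counts and follow-up time. No exact test is defined, so treating it as the conditional binomial test is an assumption, and the exact sentence may be leftover wording. This stands as evidence of intent. It does not cure the text, because the sentence still names the primary method in the section that sets the success rule.

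The fallback is also conditional. On the proxy above it could add at most 3.7 percentage points to the two-sided error even if every such trial rejected. That stands, with the limit that the proxy came from a two-arm model without the eight-country covariate.

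The re-randomisation test does not rely on variance equalling the mean, and it could expose an anti-conservative Poisson result. But it is a sensitivity analysis and does not supply the deciding interval.

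A reader might also infer that sparse secondary endpoints are where the fallback would most often be used and do most harm. The documents do not support this. Non-convergence in sparse data was not examined, and inflation grows with k × mean, so at a given dispersion low rates inflate least. The current text extends the same model to the bacteriological endpoint; Section 6.3.1.1.2 does not say so for the secondary clinical rates. Those endpoints carry no success rule.

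**Conclusion.** The defect is real but limited. The SAP gives two incompatible descriptions of the primary method and leaves the source of the 87% limit unstated, although the code points to the negative binomial model. That model held its level in the check (11.6% to 14.1%). On its usual reading the exact method does not hold it under overdispersion, and neither does the Poisson fallback as written. In the assumed range the two-sided error is about 17% to 34% instead of 13%, and the false-efficacy risk about 8% to 17% instead of 6.5%. With no overdispersion there is no inflation.

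A reader might conclude that the trial will declare efficacy far more often than 13% of the time. The documents do not support that: success lies in one direction with a nominal risk of 6.5%, only the most overdispersed scenarios pass 13%, and these figures apply only if one of the two invalid routes is actually used. Of the two, the exact wording carries more practical risk; the fallback's expected effect on the primary error rate is small.

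**What to change.** 1. Delete the sentence on exact inference in Section 6.3.1.1.1.
2. State that the 87% and 95% intervals and the p-value for VE all come from the adjusted negative binomial model.
3. State that any Poisson fallback uses a Pearson-scaled variance or a robust (sandwich) variance, and name one of the two in advance. In the check, Pearson scaling gave 12.8% to 13.4%; the robust version was not simulated.
4. Apply the same fallback wording to the bacteriological analyses in Sections 6.3.1.2 and 6.3.1.3.

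Pooling small countries before refitting is not proposed. Without a threshold fixed in advance it would add a data-driven choice.

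The cost is a wording change and one line of code, to be made before unblinding. The statistical price arises only when the fallback is used: on the log scale the interval widens by √(1 + kμ), from √1.3 = 1.14 to √2.5 = 1.58, so about 14% to 58% wider in the assumed range.

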Data will be categorized as following:

1. AECOPDs in the last 12 months managed without oral corticosteroids and antibiotics ='Mild'
2. AECOPDs in the last 12 months that required oral corticosteroids and/or antibiotics ='Moderate'
3. AECOPDs in the last 12 months that required hospitalization='Severe'

CONFIDENTIAL207489 (NTHI MCAT-002)
Statistical Analysis Plan Amendment 2 FDA Final Draft**11.2.4. Efficacy**

- **AECOPD events:** AECOPD events are confirmed according to investigator judgment after an AECOPD visit which is aimed to exclude worsening in symptoms not related to an AECOPD event.

eDiary alerts refer to daily symptoms recorded the morning after (also called morning symptoms). Alerts are based on the Anthonisen criteria:

- Worsening of two or more of the following major symptoms for at least two consecutive days*: dyspnea, sputum volume, sputum purulence (color)
Or
- Worsening of any major symptom together with any of the following minor symptoms for at least two consecutive days*: sore throat, cold (nasal discharge and/or nasal congestion), fever (oral temperature $\geq 37.5^{\circ}\text{C}$) without other cause, increased cough, increased wheeze.

* *The same two symptoms do not have to be present on both days as long as at least one major symptom is present on both days.*

AECOPD visits are scheduled after an electronic Diary Card alert confirmed by the investigator (by phone call or at the study site) or after spontaneous site visits due to worsening symptoms without any alert.

[figure not shown]
Potential AECOPD will be confirmed and registered as AECOPD event based on the following scheme:

- eDiary ALERT + phone call no confirmed = NO AECOPD event
- eDiary ALERT + phone call confirmed + site visit confirmed = AECOPD event.
- eDiary ALERT + phone call confirmed + site visit no confirmed = NO AECOPD event.
- eDiary ALERT + phone call confirmed + site visit no performed + Medical record confirmed = AECOPD event.
- eDiary ALERT + phone call confirmed + site visit no performed + Medical record no confirmed = NO AECOPD event.
- eDiary ALERT + phone call confirmed + site visit NO performed + Medical record no available = AECOPD event.
- eDiary NO ALERT + site visit NO confirmed = NO AECOPD event.
- eDiary NO ALERT + site visit confirmed = AECOPD event.
- eDiary NO ALERT + site visit NO performed + Medical record confirmed = AECOPD event.

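### The primary model uses exacerbation history only as <2 v ≥2, although the prior-year count is collected; this costs some precision on the primary vaccine efficacy.

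*SAP*

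**What the plan says.** SAP 6.3.1.1.1 models the number of moderate and severe AECOPD by negative binomial regression, with log follow-up time as offset. The covariates beside treatment are age group, country, and "GOLD grade (2, 3 or 4) and history of moderate and severe exacerbations". The code is "MODEL nb_exac = trt age gold hexac country", with hexac a two-level CLASS variable (<2, ≥2). Efficacy "will be demonstrated if the lower limit of the two-sided 87% CI of VE is above 0".

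Section 6.1.1 shows that more is known about each subject. It plans to report "history of moderate and severe exacerbation in the last 12 months" both in the two classes and as a total number, and it lists "total number of exacerbation in previous 12 months and HRQOL baseline scores" among the continuous variables to be summarised. Section 11.2.3 sorts the prior events by severity; for instance, "AECOPDs in the last 12 months that required oral corticosteroids and/or antibiotics" are classed as moderate.

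The minimisation algorithm in 11.3 uses the same two levels: "HIST_ES [2 variants]: < 2 >=2". No count-adjusted model is planned, and none appears among the sensitivity analyses.

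**The concern.** The number of exacerbations in the year before entry is the baseline value of the primary outcome. The trial title restricts entry to patients with a history of AECOPD. If that means at least one moderate or severe event in the prior year (an assumption, since the entry criteria are not in the SAP), then <2 means exactly one event, and all further variation lies inside the ≥2 class. Neither the model nor the minimisation sees it.

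Two things follow. Between-subject differences in expected rate that the count could explain stay in the dispersion parameter and widen the 87% interval on which success is judged. Chance imbalance in counts within the ≥2 class is neither prevented by design nor adjusted for in analysis.

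Elsewhere the SAP adjusts for the measured baseline: the pre-Dose 1 concentration in the antibody ANCOVA (6.4.1) and the screening score in the EXACT-PRO ANCOVA (6.6.2). Section 6.3.1.1.1 does name a baseline count, the events from enrolment to 1 month post-Dose 2. It is not in the MODEL statement, and it is measured after the first dose, so it could not serve instead.

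**Working it through.** **What can be reproduced.** The SAP gives no power, assumed efficacy, control rate or dispersion, so there is no sample-size figure to reproduce. Alpha and interval agree: 1 − 0.13 = 0.87, with z = 1.514.

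**Inputs from the SAP.** About 300 per group (section 2: "Approximately 300 subjects receiving two doses of placebo (PBS", and the same for vaccine), 1:1 allocation (11.3), one year of follow-up from 1 month post-Dose 2 (4.1), and two-sided alpha 0.13.

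**Assumptions, none from the SAP.** Every subject has 1 to 5 prior events; 10% withdraw early; true vaccine efficacy is 20%. Control rate, dispersion and the link between prior count and on-study rate vary as shown. Age, GOLD grade and country are left out.

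**Method.** 600 simulated trials per scenario, balanced within <2/≥2. Negative binomial fits with (a) treatment + two-level history and (b) the same + log(count). SE is the mean model-based SE of the log rate ratio. Extra N = (SE_a/SE_b)² − 1, from unrounded SEs. Power = Φ(−ln 0.8/SE − 1.514).

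| Share with 1/2/3/4/5 prior events (%) | Rate v prior count | Control rate | Residual dispersion | SE (a) | SE (b) | Extra N | Power a → b |
|---|---|---|---|---|---|---|---|
| 50/30/12/5/3 | ×exp(0.2) per event | 1.2 | 0.6 | 0.1041 | 0.1034 | 1.4% | 0.735 → 0.741 |
| 50/30/12/5/3 | ×exp(0.3) per event | 1.2 | 0.6 | 0.1064 | 0.1045 | 3.6% | 0.720 → 0.733 |
| 40/30/15/10/5 | ×exp(0.3) per event | 1.2 | 0.6 | 0.1073 | 0.1048 | 4.9% | 0.714 → 0.731 |
| 40/30/15/10/5 | count^0.5 | 1.2 | 0.6 | 0.1043 | 0.1037 | 1.3% | 0.734 → 0.738 |
| 40/30/15/10/5 | count^1 | 1.2 | 0.6 | 0.1099 | 0.1067 | 6.2% | 0.697 → 0.718 |
| 60/28/8/3/1 | ×exp(0.3) per event | 1.2 | 0.6 | 0.1050 | 0.1039 | 2.2% | 0.730 → 0.737 |
| 40/30/15/10/5 | count^1 | 1.2 | 0.3 | 0.0989 | 0.0949 | 8.6% | 0.771 → 0.799 |
| 50/30/12/5/3 | ×exp(0.3) per event | 0.8 | 0.6 | 0.1211 | 0.1193 | 3.0% | 0.629 → 0.639 |

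**Reading the table.**

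- SE ratios run from 1.0065 to 1.0419, so the SAP's SE is 0.7% to 4.2% larger.
- In subjects: 600 × 0.013 ≈ 8 to 600 × 0.086 ≈ 52.
- Power rises by 0.4 to 2.8 points, and by no more than 2 points in six of the eight scenarios.
- The smallest observed efficacy that meets the success rule is 1 − exp(−1.514 × SE). It moves from 14.6% to 14.5% at the small end (SE 0.1043 → 0.1037) and from 13.9% to 13.4% at the large end (0.0989 → 0.0949).
- In the second row the fitted dispersion is 0.77 with no history term, 0.67 with the two-level term and 0.59 with the count, against a true 0.6. The two-level term recovers part of the information, not all of it.
- The empirical spread of the estimates tells the same story, slightly weaker: ratios from 0.1106/0.1099 = 1.006 to 0.1022/0.0987 = 1.035. Simulated rejection rates, noisier at 600 replicates, changed by −0.4 to +3.5 points.

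**A second structure.** Here prior and on-study events share a gamma frailty that persists only in part between years (dispersion 0.4 to 1.0, prior-year rate 1.2 to 1.8, on-study rate 1.0 to 1.5, at least one prior event). Adding log(count) cuts the variance of the treatment effect by:

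- 0.3% to 2.2% if 40% of the frailty variance persists;
- 1.1% to 6.6% if 70% persists;
- 2.4% to 17.7% if all of it persists.

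At 70% persistence this is worth 600 × (1/(1 − 0.011) − 1) ≈ 7 to 600 × (1/(1 − 0.066) − 1) ≈ 42 subjects. A repeat of this calculation gave 1.1% to 7.2% at 70% persistence and 0.4% to 15% overall, with the same result for log(count) and log(1 + count).

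**The case against.** The SAP states nothing wrongly here. The four covariates beside treatment are the four minimisation factors, with history at the same two levels, and adjusting for those factors is a standard and valid choice. There is no bias and no type I error problem.

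The effect is small, and its size rests on quantities the SAP does not give. Both calculations assume that the count predicts the on-study rate within the ≥2 class, so some gain is built in and only its size is open. Age, GOLD grade and country were left out; if they correlate with exacerbation frequency, the extra gain shrinks.

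The change also reaches beyond one line. The Cox model in 6.3.1.1.2 uses the same history factor, the culture analysis in 6.3.1.3 repeats the PCR models, and the protocol may name the covariates.

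Most of this stands as a limit on size and importance. It does not remove the point: the two-level factor explains why that term is in the model, but it does not stop the count from being added beside it.

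**Conclusion.** The concern holds. History enters the primary model only as <2 v ≥2, the count is available before randomisation, and leaving it out costs precision on the endpoint that carries the success rule. This is an efficiency weakness, not an error or a source of bias.

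Under the assumptions above, a fair summary is 0.7% to 4.2% on the SE and up to about 3 points of power at an efficacy of 20%. The frailty calculation reaches further, to about 18% of variance, only if a subject's underlying rate persists fully from year to year. If the count carried nothing beyond the two classes, the loss would be near zero.

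Adding the count does not change the target. With a log link, and a baseline covariate that is independent of assignment and does not modify the effect, the adjusted and unadjusted rate ratios coincide. The permutation test in 6.3.1.1.1 holds covariates as observed and refits the model, so it works unchanged.

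**What to change.** In 6.3.1.1.1, keep hexac as the minimisation factor and add log(1 + number of moderate and severe AECOPD in the previous 12 months) as a continuous covariate. Define the count as the moderate plus severe events of 11.2.3, so that mild events do not enter. Make the same change in the bacteriological model of 6.3.1.2, which 6.3.1.3 repeats for culture. State whether the Cox model in 6.3.1.1.2 takes the same term, so that any difference in adjustment is deliberate. Record the change in section 9, and in the protocol if the covariates are named there. Fix it before unblinding.

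The cost is one covariate in two MODEL statements (three with the Cox model) and a sentence or two of text. No new data are needed.
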